4.1. Study setting

[figure not shown]
The DIPT study will take place in southwestern Uganda, where the adult HIV prevalence is 8%¹³⁶ and TB infection prevalence is estimated at 28-50%.^{137,138} Heavy alcohol use is common while other substance use is rare.¹³⁹ This is an appropriate setting for this intervention, because trials conducted in settings across Africa with similar HIV and TB prevalence have demonstrated that 6 months of IPT is effective in decreasing active TB incidence and mortality,^{3,140} in contrast to settings in southern Africa which have very high TB transmission and where longer durations of IPT may be needed.^{141,142} We will leverage the existing Uganda URBAN ARCH and SEARCH HIV clinical cohorts; each cohort will enroll 340 patients and up to 5 pilot participants.

The DIPT 1/2 cohort will be based at the Immune Suppression Syndrome (ISS) HIV Clinic of the Mbarara Regional Referral Hospital (MRRH), the site of the Uganda URBAN ARCH cohort, and its affiliate clinic, the Mbarara Municipality Clinic. There are over 12,000 active patients at the ISS Clinic; 25% are current drinkers.¹⁴³ The ISS Clinic and pharmacy use electronic medical records (EMR) that will be leveraged for patient recruitment, tracking, and active TB outcomes.

The DIPT 2/2 cohort will be enrolled from the 10 HIV clinics in southwestern Uganda taking part in the SEARCH study. Each SEARCH community is within the catchment area of a government and PEPFAR-supported ART clinic. In southwestern Uganda, >10,000 HIV+ adults are on ART at these 10 clinics, providing an ample population base for DIPT 2/2 enrollment. Among HIV+ SEARCH participants in southwestern Uganda, 27% are current drinkers. SEARCH has digitized medical records at these 10 clinics, including data on alcohol use and TB disease surveillance; this infrastructure will be leveraged for patient recruitment, tracking and HIV and TB outcomes in DIPT 2/2. Recruitment may also occur at additional HIV clinics in Southwestern Uganda as needed to meet study target enrollment.

Rationale for the two cohorts: The two cohorts in these paired U01s allow for sufficient sample size, and provide heterogeneity in clinical setting (a peri-urban Regional Referral Hospital versus rural Ugandan clinics), and in drinking patterns (primarily commercial beer versus home-brews). These two U01s also create synergy by joining together investigators focused on HIV and co-morbidities from the alcohol measurement and intervention fields ([name]) with the HIV behavioral economics and TB/HIV implementation science fields ([name]), and create a collaboration “between currently NIAAA-funded PI(s)/PD(s) with established alcohol research programs and other PI(s)/PD(s) with expertise in HIV/AIDS, and related comorbidities research, ... forming new substantial collaborations.” (RFA-AA-17-014).

Figure 1. Study schematic for 2x2 factorial trial design (Aims 1 & 2).

5. Study Procedures

5.1. Recruitment

Participants will be recruited from persons reporting alcohol use at their clinic visits.

a) DIPT1/2 participants will be recruited from HIV-infected persons at the Mbarara Municipal Clinic (MMC) in Mbarara, Uganda. Participants will also be recruited from the electronic medical records of persons attending the Mbarara ISS clinic. The AUDIT-C is conducted routinely at the initial clinic visit. Our prior studies showed that 64% of those reporting any alcohol use at initial clinic visit were heavy drinkers,¹⁰² thus ISS clinic patients reporting any alcohol use will be invited for further screening.

b) DIPT 2/2 participants will be recruited from HIV-infected persons at SEARCH clinics in southwestern Uganda, including newly diagnosed HIV-infected persons entering the cohort. We will invite adults in the SEARCH study who have reported any alcohol use (asked annually), as well as adults not participating in the SEARCH study but attending a SEARCH-associated HIV clinic, for further screening. Recruitment may also occur at additional HIV clinics in Southwestern Uganda as needed to meet study target enrollment.

For all sites of enrollment, a clinic staff member who is also a member of the research team, e.g. the screener, record room staff or clinic counselor, will initially approach those meeting these criteria. Persons meeting the initial eligibility criteria will be asked by the study screener or clinic staff member if they are interested in taking part in a research study. Those who agree will be screened to determine further eligibility criteria. The screener will review clinic medical records for potential participants, to determine preliminary study eligibility (i.e. age, no history of prior active TB, current drinker). Those who are eligible will be referred to the RA to undergo informed consent.

5.2. Screening

Eligibility screening will be a two-stage process. If preliminary eligibility is established during recruitment, a research assistant (RA) will seek informed consent for further screening to determine current heavy alcohol use confirmed by urine EtG and AUDIT-C positive for prior 3-month drinking, determine current pregnancy status (for women), rule out active TB and existing liver enzyme (ALT/AST) elevations (our prior data show mild elevations in <8% of patients), and to assess tuberculin skin test (TST) status (Figure 3). Active TB assessment will be based on the WHO 4-symptom screen,¹² with further testing (chest X-ray and/or sputum Xpert MTB/RIF assay) for those with positive symptom screens. Those diagnosed with active TB will be offered TB treatment at their local TB clinic. Patients will be asked to return in two days for TST reading.

During the second phase of screening (i.e. baseline line visit), a RA will seek informed consent from individuals who meet the inclusion criteria below for further study participation. The baseline visit will include collection of tracking information, a baseline survey, and blood draw. Liver enzyme testing will be repeated at the baseline visit if it has been longer than one month from the screening tests.

Individuals who are not eligible for the study may return to be screened again after three months.

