5.2.2. Exclusion criteria

Exclusion criteria for all sites will include:

- a) Prescribed nevirapine (NVP, an ART drug that is declining in usage due to high risk for hepatotoxicity);
- b) Initiating Dolutegravir (DTG), or has initiated DTG within the past 3 months;
- c) Plans to move out of the catchment area within 6 months;
- d) Prescribed anti-convulsion medications or history of recurring seizures;
- e) ALT or AST elevations ($\geq 2 \times$ ULN);
- f) Suspected or confirmed active TB as determined by symptom screening and followed by chest X-ray and sputum testing;
- g) History of prior active TB treatment or prior IPT.
 - As fewer than 3% of HIV-infected persons have received IPT in Africa, prior IPT will be rare.¹⁴⁴
- h) Pregnant at the time of screening
- i) Gross inebriation or inability to provide informed consent.

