5.5. Study visits

As previously described, eligibility will be a two-stage process in order to determine drinking status, TST status, and rule out active TB and liver enzyme elevations. Baseline visits will include collection of tracking information, a baseline survey (Table 2), blood draw, and repeat liver enzyme testing if it has been longer than one month from the screening tests.

[figure not shown]
Visits for INH refills and assessments for toxicity (assessment of side effects and liver enzyme testing) will occur at week 2 and months 1 through 6 for all study participants. Urine will be collected and prizes administered as described above for Arms 2, 3, and 4. Hair collection will occur at 3 and 6 months c at the time of the INH discontinuation if outside of the 3- and 6-month time point for all study participants (see below). Follow-up interviews and blood collection will occur at months 3, 6, and 12 (Table 2). Screening for symptoms of active TB, and sputum testing and chest X-ray if symptoms are reported, will occur at every follow-up visit.

Arms 2-4 only: Urine test(s) and prize(s)
↓
Month 12: Study survey, Blood draw (PEth, VL)

Retention: High retention (90% at six months, 85% at one year) will be maintained as in our prior studies using follow-up phone calls, alerts when patients come to their home clinic, and home visits when needed. To encourage high retention, participants in all study arms, including control, will receive travel reimbursements (low-value unconditional cash transfers) of up to US\$5 for attending study visits (see Figure 3).

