Urine pregnancy testing: For women of childbearing age, their screening visit urine sample will be used to test for pregnancy. Women who are pregnant at the screening visit will be excluded from the trial. Women who enroll into the trial will be asked at each follow-up visit whether they may have become pregnant. Those who answer yes will be provided a urine pregnancy test following the same procedures as the screening test.

Hair testing: INH concentrations will be measured in hair samples in all participants at 3 and 6 months. Hair collection methods have been outlined in previous papers.^{117,135,156} We will request that participants do not shave or cut their hair for one month prior to their 3- and 6-month visits; in the case that a participant does not have enough scalp hair to collect, we will schedule the participant for a hair collection visit 3-4 weeks later. Hair samples will be kept at room temperature and in a dark place prior to batch shipment (without biohazardous restrictions) to the Hair Analytical Laboratory at UCSF for INH measurement as described above.

Table 2. Schedule of study specimen and data collection.

	Eligibility	Baseline	Week 2	Month 1	Month 2	Month 3	Month 4	Month 5	Month 6	Month 12
ALT and AST testing	◆		◆	◆	◆	◆	◆	◆	◆	
CD4 count, hepatitis B surface antigen, platelet count, creatinine	◆									
HIV viral load	◆								◆	◆
Urine EtG (All Arms at Eligibility; Intervention Arms 2+4 thereafter)	◆		◆	◆	◆	◆	◆	◆	◆	

Urine IsoScreen (Intervention Arms 3+4)		◆	◆	◆	◆	◆	◆	◆
Urine Pregnancy test (women)*	◆	◆	◆	◆	◆	◆	◆	◆
INH MEMS cap data download		◆	◆	◆	◆	◆	◆	◆
Hair collection for INH level					◆			◆
DBS for PEth testing		◆			◆		◆	◆
Study interview		◆			◆		◆	◆
Assessment for active TB (symptoms, chest X-ray, Xpert if symptomatic)	◆		◆	◆	◆	◆	◆	◆

*Pregnancy test given to all women at Screening, and as-needed at follow-up visits (based on self-reported potential pregnancy)

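### Minor: when baseline falls more than a month after screening, the protocol repeats liver enzymes but neither the pregnancy test nor the TB symptom screen before isoniazid starts

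*Protocol*

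**What the plan says.** Protocol section 5.2 describes eligibility in two stages. The first stage covers pregnancy status, active TB, liver enzymes and the skin test. The second stage is the baseline visit, introduced with the words "During the second phase of screening (i.e. baseline line visit".

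The content of that visit is given twice. Section 5.2: "The baseline visit will include collection of tracking information, a baseline survey, and blood draw". Section 5.5: "Baseline visits will include collection of tracking information, a baseline survey (Table 2), blood draw, and repeat liver enzyme testing", the last item applying only after more than a month. The section 5.2 rule for a late baseline is "Liver enzyme testing will be repeated at the baseline visit if it has been longer than one month from the screening tests".

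On pregnancy, section 5.6 states: "For women of childbearing age, their screening visit urine sample will be used to test for pregnancy". After that, "Women who enroll into the trial will be asked at each follow-up visit whether they may have become pregnant", with a test only for those who answer yes. Exclusion (h) in section 5.2.2 reads "Pregnant at the time of screening".

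On TB, section 5.5 states: "Screening for symptoms of active TB, and sputum testing and chest X-ray if symptoms are reported, will occur at every follow-up visit". The first follow-up visit is week 2.

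**The concern.** Three checks clear a participant for INH: liver enzymes, pregnancy and active TB. The repeat rule accepts that a screening result can go out of date, but it acts on only one of the three. The time that makes an ALT value stale also passes for a pregnancy test and a symptom screen.

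The protocol itself names both remaining risks. Section 6.1 cites trial evidence of worse pregnancy outcomes when women with HIV take INH while pregnant, section 6.2 stops INH once pregnancy is confirmed, and section 5.2 requires active TB to be ruled out. For dolutegravir, section 6.2 ties the safety condition to enrolment. For pregnancy, the condition is tied to screening.

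What is at stake is the safety of a few participants. The validity of the trial is not in question, because these cases arise before randomisation and cannot depend on arm.

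**Working it through.** **Text comparison.** These are the written checks before and just after INH start when baseline is late:

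| Check | Screening | Baseline more than 1 month later | Week 2 (on INH) |
|---|---|---|---|
| ALT/AST | yes | repeated (5.2, 5.5) | yes |
| Pregnancy | urine test (5.6) | none written | question, test only if yes (5.6, 6.2) |
| TB symptoms | WHO four-symptom screen (5.2) | none written | yes (5.5) |

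No urine is listed at baseline. The trial-consent points in section 5.2.3 mention urine only for Arms 2 to 4 at follow-up. The footnote to Table 2 names screening and follow-up for pregnancy testing, not baseline. The grid of Table 2 is not used: the text implies nine TB assessments (eligibility, week 2, months 1 to 6, month 12), while the extracted row shows eight marks, so blank cells prove nothing.

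**Can a gap of more than a month occur?** Usually not, since participants are asked back within two to three days (5.2.3). The SAP (Impact of COVID-related disruptions) does record a pause from 19 March 2020, with enrolment resuming on 16 June 2020, 89 days later. Anyone screened before the pause and enrolled after it would exceed a month. The documents do not say whether there were such people or whether they were screened again.

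**Size (illustration).** From the documents: 680 participants, and 52% women in an earlier cohort of current drinkers (section 3.1, 48% male), so 680 × 0.52 = 354 women as the upper value. That cohort was not restricted to TST-positive heavy drinkers. Every other input is an assumption.

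Pregnancies that a repeat test would catch and that would otherwise go unrecognised = women × childbearing-age share × late-baseline share × (gap − 0.5 month test lag) × conceptions per month × unrecognised share:

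- Low: 200 × 0.60 × 0.05 × 1.0 × 0.005 × 0.5 = 0.015
- Mid: 270 × 0.75 × 0.15 × 1.5 × 0.01 × 0.75 = 0.34
- Worst: 354 × 0.85 × 0.30 × 1.5 × 0.015 × 1.0 = 2.03

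Conceptions in the two weeks before the screening test are not counted.

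TB cases that a repeat symptom screen would catch = 680 × late-baseline share × gap in years × rate per person-year × screen sensitivity:

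- Low: 680 × 0.05 × 1.5/12 × 0.005 × 0.5 = 0.011
- Mid: 680 × 0.15 × 2/12 × 0.01 × 0.65 = 0.11
- Worst: 680 × 0.30 × 2/12 × 0.03 × 0.8 = 0.82

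**Workload on the same assumptions.**

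- Strips: 200 × 0.60 × 0.05 = 6; 270 × 0.75 × 0.15 = 30; 354 × 0.85 × 0.30 = 90
- Symptom screens: 680 × 0.05 = 34; 680 × 0.15 = 102; 680 × 0.30 = 204

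**The case against.** - **Missing documents.** Figure 3, the SOPs and the screening and baseline questionnaires are not available, and a pregnancy or symptom question could well sit in one of them. This stands: the point concerns the written protocol, and practice may already be sound.
- **The exclusions can be read to cover baseline.** Baseline is called a phase of screening, so exclusion (h) can apply to a pregnancy known at that visit. Exclusion (f) carries no date and includes suspected TB, so volunteered symptoms can exclude. The main consent, taken at baseline, raises pregnancy as a reason to stop INH. This also stands, and it narrows the gap to pregnancies the woman does not know of and symptoms that nobody asks about.
- **Asking first is the trial's own standard.** During six months of INH the protocol tests only women who think they may be pregnant. On the mid assumptions, conceptions in that period would number about 270 × 0.75 × 6 × 0.01 = 12, far more than 0.34. The comparison is fair as to scale. It does not settle the matter, because before INH the protocol's standard is different: test women of childbearing age and rule out TB. A late baseline lets that standard lapse.
- **Liver enzymes are the natural thing to repeat.** They are a numerical entry threshold for hepatotoxicity, which section 6.4 calls the primary risk. This explains why they are repeated, but gives no reason to leave out two brief checks.
- **Week 2 limits the exposure.** It does so, to about two weeks, where pregnancy is suspected or symptoms are reported. A woman who does not suspect pregnancy would pass the week-2 question too.

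**Conclusion.** The gap in the written protocol is real and minor. When baseline is late, neither pregnancy nor TB symptoms are rechecked before INH starts. The expected number affected is probably below one woman and well below one TB case. The upper figures of 2.0 and 0.8 need every assumption at its worst at once. Those sizes rest on assumed values for how often baseline is late, how long the gap is, and the conception and TB rates; the documents give none of these. Confidence is medium, because unseen study materials may already close the gap. The primary analyses for Aims 1 and 2 are not materially affected.

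**What to change.** In sections 5.2 and 5.5, extend the existing rule: when more than one month has passed since the screening tests, repeat the urine pregnancy test (women of childbearing age) and the WHO four-symptom screen along with ALT/AST, before randomisation and INH dispensing. Align section 5.6 and the Table 2 footnote by adding *and at baseline if screening was more than one month earlier*. Reword exclusion (h) as *pregnant at screening or at the baseline visit*.

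The cost is a one-sentence amendment with matching wording changes, about 30 strips (6 to 90) and about 102 symptom screens (34 to 204) on the assumptions above, an extra urine sample from the women concerned, slightly longer late-baseline visits, and a few late screen failures. If the SOPs or questionnaires already require these checks, only the protocol wording needs to follow.

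If enrolment has closed, list the screening-to-baseline intervals, especially around the 2020 pause, and carry the wording into any follow-on protocol.

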5.2.1. Inclusion criteria

Trial inclusion criteria for all sites will be:

- a) HIV-infected adult (≥ 18 years) prescribed ART for at least 6 months;
- b) Current heavy alcohol use confirmed by urine EtG and AUDIT-C positive for prior 3-month drinking;
- c) Positive TST (≥ 5 mm induration);
- d) AST and ALT $< 2 \times$ the upper limit of normal (ULN);
- e) Fluent in Runyankole or English
- f) No history of active TB, TB treatment, or TB preventive therapy;
- g) Lives within 2-hour driving distance or 60 km of the study site.

5.2.2. Exclusion criteria

Exclusion criteria for all sites will include:

- a) Prescribed nevirapine (NVP, an ART drug that is declining in usage due to high risk for hepatotoxicity);
- b) Initiating Dolutegravir (DTG), or has initiated DTG within the past 3 months;
- c) Plans to move out of the catchment area within 6 months;
- d) Prescribed anti-convulsion medications or history of recurring seizures;
- e) ALT or AST elevations ($\geq 2 \times$ ULN);
- f) Suspected or confirmed active TB as determined by symptom screening and followed by chest X-ray and sputum testing;
- g) History of prior active TB treatment or prior IPT.
 - As fewer than 3% of HIV-infected persons have received IPT in Africa, prior IPT will be rare.¹⁴⁴
- h) Pregnant at the time of screening
- i) Gross inebriation or inability to provide informed consent.

5.2.3. Informed consent process

The informed consent process for both the screening and trial will take place in a private room at the ISS Clinic or research offices for the DIPT 1/2 cohort / in a private room in the clinics participating in the SEARCH study for the DIPT 2/2 cohort. The RAs will meet with eligible participants selected for recruitment to introduce the study and gauge potential subjects' interest. Potential participants will be told the purpose of the study and the reasons that they have been approached for participation.

The informed consent process will be guided by a written consent document, but will mainly consist of an interactive conversation between the RA and the potential study participant. We have separate consent forms for the screening procedures and study procedures. The RA will use the informed consent document (available in Runyakole, subjected to translation, back-translation, and revision for accuracy, clarity, and ease of comprehension) as a guide to discuss all content in the document with the potential participant. After each major section and any key points, the RA

will pause and check for understanding—for example, by asking the participant to repeat back, in their own words, what “the right to refuse” means.

Other key points to check with participants during the screening consent include: (1) they understand that the screening consent process is to assess their eligibility for the study only, and that they are not consenting to the main study; (2) they will be asked to give a urine specimen sample; (3) they will be asked to undergo blood specimen collection via venipuncture; (4) they will be asked to consent to a TST, where the RA will place a purified protein derivative (PPD) in the participant’s skin to be read 48-72 hours later; (5) they will be asked to return two-three days after the screening procedures for additional assessment including the TST reading and review of their laboratory results to determine eligibility.

Key points to check with the participants enrolling in the trial include: (1) they will be asked to undergo blood collection via venipuncture, provision of a small hair sample at 3 and 6 months after enrollment, and research assessment procedures; (2) they will be asked to repeat blood specimen collection, and urine collection (if in Arms 2, 3 or 4) and research assessment procedures at follow-up visits (week 2 and months 1, 2, 3, 4, 5, and 6 and 12) following enrollment; (3) some participants will be randomized to be eligible to receive incentives based on point-of-care urine tests that meet pre-specified criteria; (4) they will be asked to provide their name and locator information to allow the investigators to locate them for future visits; (5) they will receive a reminder call prior to their study visits; (6) they may be removed from INH if they become pregnant or develop toxicities (Grade 3 or 4); and (7) they may be asked to participate in further studies in the future.

5.3. Enrollment and randomization

After eligibility is determined, we will enroll and randomize participants, using a 2x2 factorial design, to either, both, or neither of the incentive interventions, as follows:

Arm 1: No intervention control;

Arm 2: Escalating incentives for EtG negative urine tests;

Arm 3: Escalating incentives for IsoScreen positive urine tests;

Arm 4: Escalating incentives for EtG negative urine tests and for positive IsoScreens (rewarded separately) (Figure 1).
All participants will receive brief alcohol and adherence counseling according to Uganda Ministry of Health guidelines.¹⁴⁵

Randomization will be 1:1:1:1, stratified by gender, and by study site. To ensure balance with respect to the number of participants in each arm, we will use the permuted blocks strategy (using random block sizes of 4 and 8 because the study is not double-blinded).¹⁴⁶ To allow for simultaneous enrollment at multiple sites, we will use pre-printed scratch cards revealing randomization arm as in our previous studies.

This will be an open label study as we will not be able to blind participants or research assistants to the study arm. However, we will not reveal study arm to clinic counselors and clinicians so all study arms will receive the same standard clinical and counseling procedures.

[figure not shown]
